SECONDARY OUTCOME MEASURES	
 
▪ proportion of patients with at least one episode of ventilator-associated pneumonia (VAP)
 
▪ VAP incidence density per 1000 days of mechanical ventilation
 
▪ number of VAP episodes per patient
 
▪ proportion of patients with at least one bloodstream infection (BSI) and incidence density per 1000 ICU days
 
▪ proportion of patients with at least one central venous catheter (CVC)-related infection and incidence density per 1000 CVC days
 
▪ proportion of patients with at least one urinary tract infection and incidence density per 1000 urinary-catheter days
 
▪ proportion of patients with at least one soft tissue infection and incidence density per 1000 ICU days
 
▪ proportion of patients with at least one nosocomial infection
 
▪ descriptive bacteriological data (organisms recovered and antibiotic resistance profile for each nosocomial infection)
 
▪ proportion of patients with at least one episode of vomiting
 
▪ proportion of patients with at least one episode of diarrhea
 
▪ proportion of patients with an episode of acute colonic pseudoobstruction
 
▪ proportion of patients with a documented episode of bowel ischemia
 
▪ number of calories (in Kcal) given enterally and parenterally: 
 
○ time-course of mean daily values over the first week
 
○ time-course of mean daily values throughout the time spent on mechanical ventilation
 
 
 
▪ ratio of prescribed calories over calories delivered enterally and parenterally (as percentages): 
 
○ time-course of mean daily values over the first week
 
○ time-course of mean daily values throughout the time spent on mechanical ventilation
 
○ proportion of patients in whom the calorie target was achieved on each day
 
 
 
▪ volume of feed (in mL) administered: 
 
○ time-course of mean daily values over the first week
 
○ time-course of mean daily values throughout the time spent on mechanical ventilation
 
 
 
▪ ICU mortality, hospital mortality, 90-day mortality
 
▪ mean changes in serum albumin, prealbumin, transthyretin, and C-reactive protein between study inclusion and mechanical ventilation discontinuation, day 7 (in patients on mechanical ventilation for more than 7 days), and ICU discharge
 
▪ proportion of patients with at least one episode of liver dysfunction at mechanical ventilation discontinuation, on day 7 (in patients on mechanical ventilation for more than 7 days), and at ICU discharge
 

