#### 5.10 Secondary objectives

The secondary objectives consist in comparing the following variables in the two groups:

- Nosocomial infections:
  - VAP: proportion of patients with at least one VAP episode, VAP incidence density, number of VAP episodes
  - Bacteremia: proportion of patients with at least one episode of bacteremia, incidence density of bacteremia
  - Central venous catheter (CVC)-related infections: proportion of patients with at least one CVC-related infection, incidence density of CVC-related infections
  - Urinary tract infections: proportion of patients with at least one urinary tract infection, incidence density of urinary tract infections
  - Soft tissue infections: proportion of patients with at least one soft tissue infection, incidence density of soft tissue infections
- Descriptive bacteriological data (organisms recovered and antibiotic resistance profile for each nosocomial infection)
- Proportion of patients with at least one episode of vomiting or regurgitation
- Proportion of patients with at least one episode of diarrhea
- Proportion of patients with at least one episode of constipation
- Proportion of patients with at least one episode of documented bowel ischemia
- Number of calories delivered enterally and parenterally each day
- Volume of enteral and parenteral feed delivered each day
- Ratio of prescribed over delivered calories
- ICU mortality, day-90 mortality, and hospital mortality

---

- Changes in nutritional markers during follow-up (measured at the end of mechanical ventilation, on day 7 in patients on mechanical ventilation for more than 7 days, and at ICU discharge)
- Proportion of patients with at least one episode of liver dysfunction (liver function will be evaluated at the end of mechanical ventilation, on day 7 in patients on mechanical ventilation for more than 7 days, and at ICU discharge)
- ICU stay length
- Hospital stay length
- Total time on mechanical ventilation
- Body weight changes from ICU admission to day 7 and from ICU admission to ICU discharge

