- Proportion of patients with at least one episode of diarrhea defined as liquid stools in a volume greater than 300 mL/24 hours in patients with a fecal collector or as more than four loose stools/24 hours (15).
- Proportion of patients with at least one documented episode of bowel ischemia defined as absent blood flow in one of the main arteries supplying the bowel (superior mesenteric artery, inferior mesenteric artery, or celiac artery) with evidence of bowel wall compromise on an imaging study (computed tomography angiography [CTA], angiography, or magnetic resonance angiography [MRA]) or presence of criteria for colonic ischemia according to the Favier classification system (stage I, petechiae; stage II, petechiae and superficial ulcers; and stage III, necrotic ulcers and polypoid lesions) by endoscopy (rectosigmoidoscopy or colonoscopy) (70)
- Number of calories (in Kcal) delivered enterally and parenterally:
  - daily mean during the first week
  - daily mean throughout the time on mechanical ventilation
- Ratio (as a %) of prescribed over delivered calories delivered enterally and parenterally:
  - daily mean during the first week
  - daily mean throughout the time on mechanical ventilation
  - proportion of patients who achieved their calorie target on each follow-up day
- Volume of liquid feed (in mL) delivered
  - daily mean during the first week
  - daily mean throughout the time on mechanical ventilation

- ICU mortality, 90-day mortality, and hospital mortality; to confirm deaths by day 90, we will search the epidemiological causes-of-death database (CépiDc, *Centre d'épidémiologie sur les causes médicales de décès*).
- Mean changes in serum albumin, prealbumin, transthyretin, and C-reactive protein (CRP) measured at baseline, at the end of mechanical ventilation, on day 7 (in patients on mechanical ventilation for more than 7 days), and at ICU discharge
- Proportion of patients with at least one episode of liver dysfunction during follow-up; liver function will be evaluated at the end of mechanical ventilation, on day 7 (in patients on mechanical ventilation for more than 7 days), and at ICU discharge; liver dysfunction will be defined as serum bilirubin  $>50 \mu\text{mol/L}$  and/or elevation  $>3\text{N}$  in one or more liver enzymes ( $\gamma$ -glutamyltransferase, alkaline phosphatase, and ASAT-ALAT).
- ICU stay length
- Hospital stay length
- Time on mechanical ventilation

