##### a. General principles

Nutritional support will be started as soon as possible after the initiation of invasive mechanical ventilation and no later than 24 hours after intubation or after ICU admission in patients intubated before ICU admission.

The calorie target for each patient will be estimated based on body weight as 20-25 Kcal/Kg/day during the acute phase (7 days at the most) then 25-30 Kcal/Kg/day from day 7 to extubation. In obese patients (BMI > 30 Kg/m^2), the body weight yielding a BMI of 30 will be used to estimate the calorie target.

Nutritional support will be prescribed as a flow rate (mL/hour) and started at the prescribed flow rate (as opposed to increased gradually). The feed will be delivered continuously, over the 24-hour cycle, with no interruptions. Actual feed delivery will be monitored regularly based on the volumes delivered relative to the predefined daily calorie targets. In addition, special attention will be directed to avoiding delays. Any interruption in feed delivery will be reported to the ICU physician in charge. Except in special situations, nutritional support will not be interrupted while transporting the patient. However, when enteral or parenteral nutrition must be interrupted (e.g., for a specific gastrointestinal or radiological investigation), the flow rate will not be increased to compensate for the interruption. Finally, the patient will be in the semi-recumbent supine position with the torso at 30° to 45° from the horizontal plane.

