- Second, if the intolerance persists despite prokinetic therapy, the flow rate will be decreased by 25 mL/h, every 6 hours, until the signs of intolerance resolve. Therefore, enteral nutrition will be stopped (and the gastric tube placed under suction) only in patients with intolerance despite a flow rate  $\leq 25$  mL/h. All interruptions in enteral nutrition delivery must be reported to the intensivist in charge. This precaution is particularly important in patients receiving insulin. Enteral nutrition will be resumed at the prescribed flow rate (appropriate to the patient's needs) after 6 hours have elapsed with no further signs of intolerance. (71).

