- The number of calories delivered each day by the enteral and parenteral routes: changes over time in delivered calories will be represented graphically by boxplots created each day on the same graph; changes over time will be compared between the two groups using a mixed linear model, after data transformation if necessary
- Volume of enteral and parenteral feeds delivered each day: the analysis method will be the same as for the number of calories
- Ratio of prescribed over delivered calories: the proportions of patients who achieved their daily calorie target will be determined at each follow-up time point (in days) and will be compared between the two groups using a logistic random effects model
- ICU mortality, 90-day mortality, and hospital mortality: day-90 mortality will be analyzed in the same way as day-28 mortality; for ICU and hospital mortality rates, competing-risk models will be used, as ICU discharge and hospital discharge compete with death during the stay
- Nutritional markers and body weight: changes over time in nutritional markers and body weight will be analyzed using the method described above for the number of calories delivered
- Proportion of patients with at least one episode of liver dysfunction: the method will be the same as for the primary objective
- Times in the ICU, in the hospital, and on mechanical ventilation will be compared between the two groups using nonparametric Wilcoxon tests

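### The calorie-adequacy ratio is written as prescribed over delivered, so its two daily-mean components have no value on unfed days and no upper limit on poorly fed ones

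*Combined protocol and SAP*

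**What the plan says.** Section 4.1.2 lists "Ratio (as a %) of prescribed over delivered calories delivered enterally and parenterally" with three components: a "daily mean during the first week", a daily mean over the whole time on mechanical ventilation, and the proportion of patients reaching their calorie target on each day.

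The direction is the same elsewhere:
- The synopsis outcome list has "ratio of prescribed calories over calories delivered enterally and parenterally (as percentages" and asks for the time-course of mean daily values.
- The secondary objectives (numbered 5.10 in the body, 3.2 in the contents) have "Ratio of prescribed over delivered calories".
- Section 7.1.4 has "Ratio of prescribed over delivered calories: the proportions of patients who achieved their daily calorie target will be determined at each follow-up time point", compared between groups with a logistic random effects model. It names no analysis for the mean ratio.

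Only the synopsis list of secondary objectives leaves the direction open.

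The plan expects days of low or no delivery. Section 4.2.3 a says of interruptions that "the flow rate will not be increased to compensate for the interruption". Section 4.2.3 b provides for stepwise flow reductions and then says that "enteral nutrition will be stopped (and the gastric tube placed under suction) only in patients with intolerance despite a flow rate" of 25 mL/h or less. No section says how the ratio is formed on such days.

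**The concern.** A measure of feeding adequacy should fall towards zero as less is delivered. The ratio as written does the reverse. It rises as feeding worsens, has no ceiling, and cannot be calculated on the worst days. An average of such values is driven by a few poorly fed days, while days with no feed either break the calculation or disappear, depending on a choice the plan does not make. The result can therefore look much worse or somewhat better than the feeding really was.

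The protocol's rationale (section headed 5.5) links calorie shortfall to poor outcome, so readers will want a usable adequacy figure for each arm. The two daily means are the only listed summaries that would show how far below target patients fell relative to their own needs.

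**Working it through.** The documents give no figure for this endpoint, so there is nothing to reproduce. They also give no distribution of daily delivery. Every delivery fraction below is an assumption chosen to show how the ratio behaves. Prescribed calories are assumed equal to the target.

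Let f be the fraction of the target delivered on a day. As written, the daily value is 1/f; inverted, it is f.

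**1. 100 patient-days: 90 at f = 1 and 10 at f = 0.05**
- Mean of daily ratios as written: (90 × 1 + 10 × 20)/100 = 290%.
- Mean of delivered over target: (90 × 1 + 10 × 0.05)/100 = 90.5%.
- Summed prescribed over summed delivered calories: 100/90.5 = about 110%.

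**2. 100 patient-days: 80 at f = 1, 10 at f = 0.10 and 10 at f = 0**
- As written: undefined. If the unfed days are dropped (a further assumption): (80 × 1 + 10 × 10)/90 = 200%.
- Delivered over target: (80 + 1 + 0)/100 = 81%.
- Summed calories with the unfed days kept: 100/81 = about 123%.

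**3. One patient-week: six days at f = 1 and one poor day**

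| Poor day, % of target | Mean as written, (6 + 1/f)/7 | Summed calories, 7/(6 + f) | Mean delivered/target, (6 + f)/7 |
|---|---|---|---|
| 50 | 114.3% | 107.7% | 92.9% |
| 10 | 228.6% | 114.8% | 87.1% |
| 5 | 371.4% | 115.7% | 86.4% |
| 1 | 1514.3% | 116.5% | 85.9% |
| 0 | undefined; 100% if the day is dropped | 116.7% | 85.7% |

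**4. Three sets of 10 patient-days, each with 80% mean adequacy**
- All ten at 80%: 1/0.8 = 125.0%.
- Seven at 100%, two at 47.5%, one at 5%: (7 + 2/0.475 + 20)/10 = 312.1%.
- Seven at 100%, two at 50%, one at 0%, unfed day dropped: (7 + 4)/9 = 122.2%.

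The same adequacy can thus read as 122%, 125% or 312%. The third set, which contains an unfed day, looks better than the uniform one.

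**5. Ratio by route.** If calories are taken separately by route, the parenteral ratio in the enteral group has no denominator in the first week, because section 4.2.4 allows supplemental parenteral nutrition there only from day 8.

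**6. Available data.** Section 4.6 collects the target number of calories and the calories delivered, every day until extubation. It does not list prescribed calories. The section 4.2.7 flowchart defines D0 as running from inclusion to 11:59 pm, so it is a partial day.

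**The case against.** The strongest reply is that little depends on these two means. Under the ratio heading, section 7.1.4 plans one between-group comparison, the daily proportion on target. This does not depend on the direction of the ratio, and an unfed day can simply count as target not reached. Section 7.1.4 also compares delivered calories and volumes over time with mixed linear models, where zero is a valid value. Both arms share the same weight-based target, so delivered calories already show feeding by arm. All of this stands, and it confines the problem to two summaries with no stated test.

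It is also fair that the large figures need an average of individual daily ratios. The text says only daily mean or mean daily values, and a ratio of summed calories removes most of the inflation. Since the plan does not say which is meant, this limits the size of the problem without curing the definition.

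A reader might infer that unfed days will be dropped, that they fall mainly in the enteral arm, and that the adequacy comparison needed to interpret mortality is therefore distorted differently by arm. The documents do not establish this:
- They are silent on unfed days.
- Feed is stopped only after a prokinetic and stepwise reductions, and resumes after 6 hours without intolerance, so whole days at zero may be uncommon.
- Parenteral feed can be interrupted too.

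A difference between arms is plausible, because the intolerance rule applies to enteral feed and supplemental parenteral nutrition in that group waits until day 8. It is not quantified.

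**Conclusion.** The definition is wrong as written, and consistently so, which makes an isolated slip unlikely. The two daily-mean components are undefined on days without delivery and unbounded on days with little, and no rule covers either case. In the assumed 90/10 example the mean of daily ratios is 290% against a true adequacy of 90.5%, or about 110% if calories are summed. These sizes rest on assumed delivery fractions and are not predictions for this trial.

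The importance is minor. The proportion on target, the delivered-calorie and volume analyses, day-28 mortality and the sample size are untouched. The documents do not support a claim that the arms will be compared unfairly or that the mortality result becomes harder to interpret.

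**What to change.** Use one definition in all five places: both synopsis lists (secondary objectives and secondary outcome measures), the secondary objectives section, 4.1.2 and 7.1.4.

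- Define the ratio as delivered calories over the predefined daily calorie target, as a percentage. The target is a better denominator than prescribed calories: it is collected daily, whereas the plan does not say whether the prescription falls when the flow rate is cut for intolerance. If it does, delivered over prescribed would stay near 100% and hide underfeeding.
- Count a day without delivery as 0% while the patient is still under the nutritional-support protocol.
- Handle the partial day D0 separately, so that a short day is not read as underfeeding.
- State that the mean is of daily percentages, whether the two routes are combined, and whether the mean is descriptive or has a named analysis.

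The cost is wording only. Section 4.6 already collects the target and the delivered calories each day, so no new data are needed.

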#### Laboratory data

- D1: hemoglobin, leukocytes, platelets, Na, K, Ca2+, Ph, PaO2, PaCO2, pH, arterial lactic acid, bicarbonate, urea, creatinine, bilirubin, ASAT-ALAT, gamma-glutamyl transpeptidase, alkaline phosphatase, and total protein
- Daily from D1 to D7 (if extubation before D7: on the day of extubation then stop): PaO2, arterial lactic acid, bilirubin, ASAT-ALAT, gamma-glutamyl transpeptidase, alkaline phosphatase, glucose, protein, Na, K, Ca2+, Ph, creatinine, and SOFA
- Albumin, pre-albumin, transthyretin, and CRP on D1 and D7 or on the day of extubation

Nosocomial infections (one data-collection form per infection): VAP (date, organism, resistance profile), bacteremia (date, organism, resistance profile), intravascular catheter-related infection (date of the diagnosis, organism, resistance profile), urinary tract infection (date of the diagnosis, organism, resistance profile), soft tissue infection (date of the diagnosis, organism, resistance profile); and other (type, date of the diagnosis, organism, resistance profile).

Invasive devices: endotracheal tube (dates of insertion and removal), intravascular catheters (dates of insertion and removal), and urinary catheters (dates of insertion and removal)

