### 5.17 Noninclusion criteria to be absent in study participants

- Invasive mechanical ventilation started more than 24 h earlier
- Patient admitted for an acute gastrointestinal condition that contraindicates enteral nutrition
- Surgery on the gastrointestinal tract within the past month
- History of gastrectomy, esophagectomy, duodenopancreatectomy, bypass surgery, gastric banding, or short bowel syndrome

---

- Gastrostomy or jejunostomy
- Specific nutritional needs, such as pre-existing long-term home enteral or parenteral nutrition
- Active gastrointestinal bleeding
- Dying patient – not-to-be-resuscitated order or other treatment-limitation decision at ICU admission
- Adult under guardianship
- Pregnancy, recent delivery, or lactation
- Department of corrections inmate
- Institutionalized patient
- Prior inclusion in a randomized trial designed to compare enteral and parenteral nutrition
- Contraindication to parenteral nutrition: known hypersensitivity to egg or soybean proteins or to another component, inborn error in amino-acid metabolism, or severe familial dyslipidemia affecting triglyceride levels

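### Liver dysfunction that predates feeding and persists to a listed check counts as an event in both arms, which attenuates this secondary comparison and costs it power

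*Combined protocol and SAP*

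**What the plan says.** All references are to the combined protocol and SAP.

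- **Event.** Section 4.1.2 lists "Proportion of patients with at least one episode of liver dysfunction during follow-up". The limits are absolute: "liver dysfunction will be defined as serum bilirubin" above 50 µmol/L, and/or more than 3N in at least one of gamma-glutamyltransferase, alkaline phosphatase and ASAT-ALAT. There is no new-onset or worsening rule. The synopsis and section 5.10 (secondary objectives) add none.
- **When it is assessed.** In section 4.1.2, "liver function will be evaluated at the end of mechanical ventilation, on day 7" for patients ventilated for more than 7 days, and at ICU discharge. Inclusion is not a listed assessment.
- **Analysis.** Section 7.1.4: "Proportion of patients with at least one episode of liver dysfunction: the method will be the same as for the primary objective". Section 7.1.3 makes that a chi-square test, with no adjustment named. Section 7.1.2 keeps every patient in the randomised group.
- **Eligibility.** Sections 5.16 and 5.17 require ventilation and a vasoactive amine, and exclude neither liver disease nor abnormal liver tests. The nearest item, "Contraindication to parenteral nutrition: known hypersensitivity to egg or soybean proteins or to another component", names no liver condition.
- **Contrast.** The same list in section 4.1.2 does use a starting value for other markers: "Mean changes in serum albumin, prealbumin, transthyretin, and C-reactive protein (CRP) measured at baseline".
- **Early liver tests.** Section 4.6 (Laboratory data) collects "bilirubin, ASAT-ALAT, gamma-glutamyl transpeptidase, alkaline phosphatase, and total protein" on D1, then liver tests daily to D7 or to extubation if earlier. The flowchart in section 4.2.7 also marks laboratory tests at D0, which it defines as the time from inclusion to the end of that calendar day.

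**The concern.** Dysfunction that exists before feeding starts cannot have been caused by the feeding route. The population is in shock and ventilated, and nothing in the eligibility criteria keeps patients with abnormal liver tests out. If such a patient is still above the limit at a listed assessment, the endpoint counts an event that carries no information on route.

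Randomisation spreads these patients evenly in expectation, so the test remains valid. But adding the same share of events to both arms shrinks the risk difference, pulls the risk ratio towards 1 and adds variance. For an unwanted outcome, the practical danger is that a real difference between routes is reported as no difference. The plan collects early liver tests and does not use them here.

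**Working it through.** **1. The plan's own figure.** Section 7.2 gives 37% against 32%, alpha 4.9% and beta 20%. Two-sided, with pooled variance and no continuity correction:

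n = [1.9686 × √(2 × 0.345 × 0.655) + 0.8416 × √(0.37 × 0.63 + 0.32 × 0.68)]² / 0.05² = 1426.5, so 1427 per arm. This matches. The plan states no size or power for the liver endpoint. The same test and alpha are used below with n = 1427.

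**2. Inputs not in the documents (assumptions).**
- New dysfunction, p: 14% in one arm and 10% in the other (risk ratio 1.40, difference 4.0 points).
- Share above the limits before feeding, b: 10%, 20%, 30%.
- Share of those still above the limits at a listed assessment, q: 0, 0.25, 0.5, 1.
- Baseline cases that resolve are given the same new risk p as everyone else.

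**3. Formulas.**
- Observed risk in an arm = bq + (1 − bq)p, so the risk difference is multiplied by (1 − bq).
- Power = Φ{[d√n − 1.9686 × √(2m(1 − m))] / √(P(1 − P) + E(1 − E))}, with P and E the observed risks, d their difference and m their mean.
- New-onset analysis: risks 14% and 10%, with 1427(1 − b) per arm, i.e. 1284, 1142 and 999.

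**4. One case in full** (b = 0.20, q = 0.5, so bq = 0.10).
- P = 0.10 + 0.90 × 0.14 = 0.226 and E = 0.10 + 0.90 × 0.10 = 0.190.
- Difference 0.036; risk ratio 0.226 / 0.190 = 1.19.
- Power = Φ[(0.036 × 37.776 − 1.9686 × 0.5740) / 0.5734] = Φ(0.401) = 65.6%.

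**5. All cases** (risk ratio; power).

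| Analysis | b = 10% | b = 20% | b = 30% |
|---|---|---|---|
| As written, none persist | 1.40; 90.7% | 1.40; 90.7% | 1.40; 90.7% |
| As written, a quarter persist | 1.32; 84.6% | 1.26; 78.0% | 1.22; 71.6% |
| As written, half persist | 1.26; 78.0% | 1.19; 65.6% | 1.14; 54.9% |
| As written, all persist | 1.19; 65.6% | 1.11; 46.2% | 1.08; 33.3% |
| New onset, patients below the limits at baseline | 1.40; 87.6% | 1.40; 83.5% | 1.40; 78.3% |

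The corner b = 30%, q = 0.5 is 0.269 / 0.235 = 1.14.

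**6. Reading the table.** From a quarter persisting upwards, the new-onset analysis has more power in every column. If none persist, the endpoint as written is undiluted and the new-onset analysis is the weaker of the two, because it uses fewer patients.

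**The case against.** The strongest objection is to the remedy. The laboratory list in section 4.6 starts at D1, and the flowchart has a separate D0 before it, so D1 appears to be the day after inclusion. Section 4.2.3 starts feeding within 24 hours of intubation or ICU admission, at the full prescribed rate. Many D1 panels could therefore be drawn on allocated feed. Excluding or stratifying patients on such a value conditions on something the route may already have changed, a fault the present endpoint does not have. This stands, and it governs the choice of baseline. It does not remove the dilution.

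Four stronger readings are tempting and are not supported:

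- *Every patient abnormal at inclusion is an event.* Inclusion is not a listed assessment. A prior case counts only if it is still above the limits at a later listed check, so full persistence is the upper bound.
- *The comparison is biased towards one arm, or its type I error is raised.* Prior cases are balanced by randomisation in expectation.
- *The protocol itself links hepatobiliary harm to the feeding route.* Section 6.1 ties it to overnutrition, and sets the same calorie target in both arms to avoid that.
- *This is a key safety endpoint.* It is one of many unranked secondary endpoints, with no power claim.

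**Conclusion.** The concern holds in a limited form. The definition lets persisting, pre-feeding dysfunction count in both arms, and nothing in the analysis corrects for it. The consequence is a risk ratio pulled towards 1 and lower power on one secondary endpoint.

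The size depends on three quantities that the documents do not give: incidence, baseline prevalence and persistence. Under the assumed 10% against 14%, with 10% to 30% affected at baseline, the loss runs from nothing (none persist) to a risk ratio of 1.08 with 33% power (30% affected, all persisting). No single cell of the table should be quoted as the expected loss. The primary endpoint and its sample size are untouched.

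**What to change.** 1. **Name the baseline.** Use the last liver panel drawn before study feeding starts. The D0 laboratory tests in the section 4.2.7 flowchart are the natural source, but D0 runs to the end of the inclusion day, so the sample time must be checked against the start of feeding. Reconcile the flowchart with section 4.6, which lists the panel only from D1. Do not condition on a D1 value drawn after allocated feeding began.
2. **Main analysis.** Keep all randomised patients and adjust for baseline dysfunction status, by logistic regression or Mantel-Haenszel.
3. **Second analysis.** Report new-onset dysfunction among patients below the limits at baseline. This is where the undiluted effect is read, since an adjusted estimate still averages over patients already affected.
4. **Supportive.** Show the unadjusted all-patient proportion as now planned.

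**Cost.** A few sentences in sections 4.1.2 and 7.1.4, and no new sampling where a pre-feeding panel exists. The new-onset analysis drops patients already affected, and patients without a pre-feeding panel need a missing-baseline category. Section 7.6 leaves the plan open until database lock. Because the trial is open, the change should be made without sight of liver results by arm.
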